## 5.8 Randomization/Drug Assignment

---

All subjects will be assigned a unique identification number by the IRT at the Screening Visit. For subjects who rescreen, the screening number assigned by the IRT at the initial screening visit should be used. The IRT will assign a randomization number that will encode the subject's treatment group assignment according to the randomization schedule generated by the statistics department at AbbVie.

Subjects will be randomized in a 1:1 ratio to one of two treatment groups:

- Treatment A: Upadacitinib 30 mg + placebo pre-filled syringe (N = 325)
- Treatment B: Dupilumab 300 mg + placebo tablets (N = 325)

Randomization will be stratified by baseline disease severity (moderate [vIGA-AD 3] vs. severe [vIGA-AD 4]) and age (< 40, ≥ 40 to 65, ≥ 65 years).

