## 7.3 Statistical Analyses for Efficacy

---

All efficacy endpoints will be analyzed in the ITT population to test the superiority of upadacitinib over dupilumab. In addition, the primary efficacy endpoints will be analyzed in the Per Protocol Population, if defined. Subjects will be included in the treatment group to which they are randomized.

Categorical variables will be analyzed using Cochran-Mantel-Haenszel (CMH) test, stratified by vIGA-AD categories (vIGA-AD 3 or 4). Continuous variables will be analyzed using mixed-effect model with repeated measures (MMRM).

Missing values and visits after the rescue will be handled by non-responder imputation (NRI) for categorical variables (except for missing values due to COVID-19, which will be handled by multiple imputation, NRI-C) or MMRM for continuous variables.

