### Primary Analysis

The primary endpoint is the proportion of subjects achieving EASI 75 at Week 16.

Comparison of the primary endpoint will be made between the upadacitinib group and the dupilumab group using the CMH test, stratified by vIGA-AD categories. NRI-C will be the primary approach to handle missing values, with multiple Imputation (MI) as the sensitivity approach to handle missing values. Per-protocol analysis, if defined, will be used as another sensitivity analysis.

Secondary endpoints will be analyzed in the ranked order as outlined in Section 3.3.

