2.3 Treatment Assignment and Blinding

Subjects will be randomized to upadacitinib or dupilumab in a 1:1 ratio. Randomization will be stratified by baseline disease severity (moderate [vIGA-AD 3] vs. severe [vIGA-AD 4]), and age (< 40, \geq 40 - < 65, \geq 65).

The AbbVie study team, study site personnel, and subjects will be blinded to treatment assignment until the primary analysis. Thereafter, all study site personnel involved in the study and subjects will remain blinded to the subject's treatment throughout the study. The exception to this is the designated unblinded site staff responsible for administration of the injectable study drug who are unblinded for the entirety of the study.

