4.0 Analysis Populations

The following populations will be used for the analyses.

The Intent-to-Treat (ITT) Population includes all randomized subjects. The ITT Population will be used for all efficacy analyses. Subjects will be included in the analysis according to the treatment groups that they are randomized to.

The Per-Protocol (PP) Population will include ITT subjects which excludes subjects with major protocol deviations that potentially affect the primary efficacy endpoint. The final criteria and the exclusion of subjects from the per-protocol population will be finalized before unblinding data for the Primary Analysis.

The Per-Protocol Population will exclude the subjects who violate any of the following criteria:

- Receive 80% of planned study drug, per randomization, before Week 16
- Have an EASI assessment post-baseline on or before Week 16
- Meet all the following disease activity criteria:
 - EASI score ≥ 16 at the Baseline Visits;
 - vIGA-AD score ≥ 3 at the Baseline Visits;
 - $\geq 10\%$ BSA of AD involvement at the Baseline Visits;
 - Baseline weekly average of daily worst pruritus NRS ≥ 4 . Note: The baseline weekly average of daily worst pruritus NRS will be calculated from the 7 consecutive days immediately preceding the Baseline Visit. A minimum of 4 daily scores out of the 7 days is needed.
- Must not have used the following AD treatments within the specified timeframe prior to Baseline Visit, per assessment of eligibility criterion 16 in the protocol:
 - Systemic therapy for AD, including but not limited to corticosteroids, methotrexate, cyclosporine, azathioprine, phosphodiesterase type 4 (PDE4)-inhibitors, interferon-gamma (IFN- γ) and mycophenolate mofetil within 4 weeks;
 - Targeted biologic treatments (refer to Section 5.3 of the protocol) within 5 half-lives [if known]) or within 12 weeks, whichever is longer;

- Phototherapy treatment, laser therapy, tanning booth, or extended sun exposure that could affect disease severity or interfere with disease assessments within 4 weeks;
- Oral or parenteral traditional Chinese medicine within 4 weeks;
- Marijuana use within 2 weeks;
- Topical treatments (with the exception of topical emollient treatments, described in Eligibility Criterion 8), including but not limited to TCS, TCIs, or topical PDE-4 inhibitors within 7 days.

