8.0 Efficacy Analyses

8.1 General Considerations

The Primary Analysis will be performed after all ongoing subjects have completed the Week 24 visit and the database has been locked. This will be the only and final analysis for the primary and key secondary efficacy endpoints as well as all other efficacy endpoints. All efficacy analyses will be conducted in the ITT Population. In addition, Per-protocol analysis for primary endpoint will be performed. All tests will be 2-sided at an alpha level of 0.05.

Categorical variables and continuous variables will be analyzed using Cochran-Mantel-Haenszel (CMH) and Mixed-Effect Model Repeat Measurement (MMRM) method, respectively.

"Baseline" refers to the last non-missing observation before the first administration of study drug or randomization if no study drug is given. When analyzing rolling-average-based endpoints, Baseline refers to the last available rolling average before the date of first administration of study drug.

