8.1.1 Analysis of Efficacy Endpoints by Variable Type

Analysis of Categorical Variables

For ITT Population, frequencies and percentages will be summarized along with 95% confidence interval (CI) based on normal approximation. For ITT Population, pairwise comparisons of upadacitinib vs. dupilumab will be made using CMH test using stratification factor as baseline vIGA-AD categories (vIGA-AD 3 or 4). Point estimates, *p*-value, and 95% CIs for the difference in proportions between upadacitinib and dupilumab will be provided. Construction of CIs for the common risk difference will be based on the Mantel-Haenszel estimate adjusting for stratification factors. Breslow-Day test will be performed to test the homogeneity between strata.

NRI-C will be the primary approach for categorical endpoints (Section 8.2). In addition, the primary endpoint and all key secondary categorical endpoints will be analyzed using MI defined in Section 8.2 as the sensitivity approach. All categorical endpoints will be analyzed using NRI-NC defined in Section 8.2 as the sensitivity approach.

Analysis of Continuous Variables

For ITT Population, the Baseline and visit means will be presented for each treatment group who have both Baseline and post-baseline visit values. For ITT Population, Percent change from Baseline in the treatment groups will be compared using MMRM model as described in Table 1. Point estimates, SE, and 95% CIs of LS mean change from Baseline within treatment groups, and these statistics along with *p*-value between upadacitinib group and dupilumab will be provided.

Table 1. Model of Continuous Variables

Population	Model	Adjust for Stratification Factor(s)
ITT	MMRM model includes the categorical fixed effects of treatment, visit and treatment-by-visit interaction, and the continuous fixed covariates of Baseline measurement.	vIGA-AD categories at randomization

All efficacy endpoints will be analyzed overall and within each stratum of the stratification factors: baseline vIGA-AD categories and age group Analysis model within each stratum will not be adjusted for stratification factors.

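### Randomisation is stratified by vIGA-AD and age, but the CMH, MMRM and imputation models adjust for vIGA-AD only: a minor point that can be put right without new data

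*SAP*

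**What the plan says.** **Randomisation.** SAP 2.3 states: "Randomization will be stratified by baseline disease severity (moderate [vIGA-AD 3] vs. severe [vIGA-AD 4]), and age". There are three age groups, so two by three gives six strata. Protocol 4.1, Protocol 5.8 and SAP 2.2 give the same two factors. Protocol 5.8 prints the upper age groups as "≥ 40 to 65, ≥ 65 years", which overlap at 65. Protocol 4.1 and SAP 2.2, 2.3, 7.1 and 8.6 end the middle group below 65.

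**Analysis.**
- Primary and other categorical endpoints: SAP 8.1.1 specifies a "CMH test using stratification factor as baseline vIGA-AD categories (vIGA-AD 3 or 4"), and SAP 8.3.3 repeats vIGA-AD alone. Protocol 7.3 agrees: "stratified by vIGA-AD categories (vIGA-AD 3 or 4") in general, and "using the CMH test, stratified by vIGA-AD categories" for the primary endpoint.
- Continuous endpoints: the MMRM adjusts for "vIGA-AD categories at randomization" (SAP 8.1.1, Table 1). SAP 8.2.2 says the same and calls this the main stratification factor.
- Imputation: the multiple imputation models in SAP 8.2.1 and Appendix F 2.3 contain treatment, vIGA-AD, gender, Baseline and the visit values, but not age.
- Age enters only through analyses within age strata (SAP 8.1.1) and subgroups (SAP 8.6). No section says why it is left out of the adjusted models.

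**Population and Baseline.** "The Intent-to-Treat (ITT) Population includes all randomized subjects" (SAP 4.0). Baseline "refers to the last non-missing observation before the first administration of study drug" (SAP 8.1). SAP 12.0 records that some subjects entered with vIGA-AD below 3; it does not say how many.

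**The concern.** Stratified randomisation forces the arms to be alike on the stratification factors. If a factor predicts the outcome, the treatment estimate varies less than an analysis ignoring that factor assumes, and the reported standard error is too large. The error is conservative: confidence intervals are a little wide and power is a little low. Neither the estimate nor the type I error is put at risk.

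The wording of the strata is also loose.
- The CMH text does not carry the at-randomisation qualifier that the MMRM has. If Baseline is read as in SAP 8.1, a subject who entered with vIGA-AD below 3 belongs to neither category 3 nor category 4.
- SAP 8.1.1 uses the singular factor for the CMH test but the plural for the confidence interval of the common risk difference, and later in the same section lists both vIGA-AD and age as the factors. Read literally, the test and its interval could use different strata.
- The sample code in Appendix F imputes with `VIGAN` but analyses by `STRATAN`, which is not defined in the text shown.

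**Working it through.** **1. The plan's own figure.** SAP 2.4 gives 325 per arm, 50% against 62% and two-sided alpha 0.05.
- Null SE = √(2 × 0.56 × 0.44 / 325) = 0.0389.
- Alternative SE = √((0.50 × 0.50 + 0.62 × 0.38) / 325) = 0.0387.
- z = (0.12 − 1.96 × 0.0389) / 0.0387 = 1.13, so power is 87.1%. The stated power of more than 80% is reproduced.

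**2. Size by hand.** Assumed, because the documents do not say: half the subjects have vIGA-AD 4, with response 10 points lower; response falls linearly over the age groups by 30 points in all; the age mix is 62/32/6%.
- Mean outcome variance within an arm: (0.2500 + 0.2356)/2 = 0.2428. Less the part explained by vIGA-AD, 0.5 × 0.5 × 0.10² = 0.0025, this leaves V = 0.2403.
- With the 6% aged 65 or over pooled into the middle group, the older group lies (0.32 × 0.15 + 0.06 × 0.30)/0.38 = 0.174 below the youngest. The part explained by age is B = 0.62 × 0.38 × 0.174² = 0.0071.
- Excess SE when age is ignored: √(V/(V − B)) − 1 = √(0.2403/0.2332) − 1 = 1.5%.
- B scales with the square of the fall. At 20 points the excess is 0.7%, at 10 points 0.2%, at 0 none.
- With an age mix of 50/40/10%, B at 30 points is 0.0081 pooled (excess 1.7%) or 0.0099 unpooled (excess 2.1%).

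**3. Simulation of the planned estimator.** There were 200,000 trials of 650 subjects per scenario, with permuted blocks of 4 (assumed) within the six strata. Each was analysed by the Mantel-Haenszel risk difference with Sato variance and a Wald test. There were no COVID-19 missing data, so the Appendix F 2.5.2 statistic reduces to this z. The comparison is vIGA-AD only against vIGA-AD × age, pooling the oldest group when it holds under 10%.

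| Fall, youngest to oldest | Excess SE, 62/32/6% | Power, 62/32/6% | Excess SE, 50/40/10% | Power, 50/40/10% |
|---|---|---|---|---|
| 0 points | 0.0% | 87.6 → 87.6% | 0.0% | 87.7 → 87.7% |
| 10 points | 0.2% | 87.8 → 87.8% | 0.2% | 87.7 → 87.7% |
| 20 points | 0.7% | 87.8 → 87.9% | 0.8% | 88.0 → 88.2% |
| 30 points | 1.5% | 88.2 → 88.6% | 1.9 to 2.0% | 88.2 → 88.8% |

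Type I error was 4.9 to 5.3% with vIGA-AD only and 5.0 to 5.3% with age added. Interval coverage at 30 points was 95.3% and 94.9%. The empirical SD of the estimate was the same (0.03781 and 0.03780), so what improves is the reported SE, not the estimate.

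**4. Stronger age effects, six strata, no pooling.** A separate simulation (5,000 to 10,000 trials per scenario; 2, 5 or 10% aged 65 or over) used an odds ratio per age step and the CMH test.
- Odds ratio 1.0: power changed by −0.1 to −0.2 points.
- 0.78: +0.1 to +0.2 points.
- 0.61: +0.2 to +0.3 points.
- 0.37: +1.0 to +1.5 points. Type I error was 4.4 to 4.5% with vIGA-AD only and 4.9 to 5.6% with six strata (simulation error about 0.2 to 0.3 points).

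An odds ratio of 0.37 per step is extreme: 60% response in the youngest group becomes odds of 1.5 × 0.37² = 0.205, or 17%, in the oldest.

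**5. Entrants with vIGA-AD below 3.** Only if the observed value were used and these subjects dropped would they be lost. Putting (650 − k)/2 per arm into the formula of step 1, k = 1, 5, 10 or 30 gives power of 87.0, 86.8, 86.6 or 85.5%.

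**The case against.** The strongest reply is that nothing here is defective. The choice is prespecified, protocol and SAP agree, and it looks deliberate: Table 1 lists vIGA-AD alone and SAP 8.2.2 calls it the main factor. The estimate is no more precise with age added, and the visible gains need age effects of 20 to 30 points that no section supports. Age is already examined within strata and subgroups. All of this stands and keeps the point minor. But stratum-specific and subgroup results do not correct the standard error of the overall comparison.

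On wording, the randomised stratum is the natural reading for the CMH test, and where the SAP groups observed vIGA-AD (7.1 and 8.6) it gives values below 3 a place. The loss of subjects in step 5 is therefore a hypothetical. The age cut in Protocol 5.8 is probably a slip and does not touch the planned CMH test. These items are clarifications and would not justify a comment by themselves.

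On cost, the change is a late departure from Protocol 7.3. SAP 2.0 is dated 2 November 2020. If LSFV in Appendix E (5 May 2020) is the last subject's first visit, then 35 days of screening plus 112 days put the last Week 16 in late September 2020. The change is defensible only if made blind and logged. The pooling rule could go either way when about 10% are aged 65 or over (it applied in 48% of simulated trials with the 50/40/10% mix), but step 2 shows the result hardly depends on it. Finally, the figures cover the risk difference with complete data; none was computed for the MMRM or the imputation models.

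**Conclusion.** The point holds and is minor. The efficacy models omit one of the two factors used to randomise, and no reason is given. The consequence is conservative: a reported standard error 0 to about 2% too large, and power lower by 0 to about 0.6 points, for age falls of 0 to 30 points. Under a much steeper age effect the power loss reaches about 1.5 points. If age does not predict response, adding it costs at most about 0.2 points. There is no bias, no type I inflation and no change to the sample size.

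The size rests on an assumed age mix, age effect, vIGA-AD split and block size, none of which the documents give. That the omission does not inflate type I error rests on the stratified design and not on those figures.

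**What to change.** Before unblinding:
- State in SAP 8.1.1, 8.2 and 8.3.3 that the CMH test, the Mantel-Haenszel risk difference, the MMRM and the imputation models use the stratum recorded in the IRT at randomisation (vIGA-AD 3 or 4 × age group). Every ITT subject then has exactly one stratum, fixed before treatment.
- Write a mechanical pooling rule now: combine age 65 or over with the adjacent group when it holds under 10% of subjects, as SAP 8.6 does for subgroups, or when a vIGA-AD × age cell is empty in either arm. The 10% condition can be settled on blinded counts.
- Confirm the age cut programmed in the IRT and reconcile Protocol 5.8 with Protocol 4.1 and SAP 2.3.
- Define `STRATAN` and `VIGAN` in Appendix F to match.
- Log the departure from Protocol 7.3 in SAP 12.0.

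The cost is wording in these places and one logged departure. No new data are needed, because both factors were collected to randomise. At an assumed 6% aged 65 or over, four strata would be analysed instead of six.

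If the sponsor prefers to keep the protocol analysis, the minimum is to say in SAP 8.1.1 and 8.3.3 that the CMH stratum is vIGA-AD as recorded at randomisation. Defining `STRATAN` would still be worthwhile.

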8.1.2 Analysis of Daily Efficacy Measurements

For daily efficacy assessments including the Worst Pruritus NRS, a rolling weekly average is calculated by using handheld device only to represent the corresponding endpoints by week on and before Week 16.

The weekly average of the daily values from a maximum of seven days immediately prior to the first dose date will be used as the Baseline value. The rolling weekly average score is calculated for each Day m , starting from Day 8 through the Week 16 visit or Study Day 120 as follows. Let $P_{m-6}, P_{m-5}, \dots, P_{m-1}, P_m$ be the daily score from Day $m-6$ to Day m , and N_m be the number of days with non-missing scores from Day $m-6$ to Day m , then the rolling weekly average for Day m is:

$$\frac{\sum_{i=m-6}^m P_i}{N_m}$$

If the values from four or more days of the seven-day period are missing, then the rolling weekly average of Day m will be set to missing. If more than one assessment is included on the same day, the assessment associated with the worst condition on that day will be

chosen as the daily score. Analysis value for a given visit will be selected from rolling averages based on analysis window conventions.

For the visits where the questionnaire is completed at the site, scores from single clinic visits will be used as the analysis value. However, these analysis values will not be included in rolling weekly average calculations.

8.2 Handling of Missing Data

Missing data could occur due to various reasons, including missing visits/assessments, early withdrawal from the study, or missing due to COVID-19 infection or logistic restriction.

The COVID-19 pandemic is interfering with the conduct of many ongoing trials, with potential impacts on treatment duration and the collection, analysis and the interpretation of clinical trial data. Some protocol-specified visits in the clinical trials may be impacted due to COVID-19 infection or logistical restrictions during the pandemic. For example, some scheduled visits may be missed due to self-quarantine or local government restrictions on travel; some visits may also be delayed or canceled due to healthcare resource constraints during the pandemic. Impacted visits due to COVID-19 will be recorded in the database. The probability of having missed visits and missing data due to COVID-19 infection or logistical restrictions related to the COVID-19 pandemic can be reasonably assumed to be unrelated to the unobserved values. Therefore, for the purpose of statistical analysis, it is reasonable to assume that these missing data are missing at random (MAR) and the statistical models that require MAR assumption are appropriate. Sensitivity analyses will be performed to assess the impact of missing data and the robustness of the conclusion.

Handling of intercurrent events and missing data for the efficacy analyses is described below:

8.2.1 Categorical Endpoints

- The primary approach for handling missing data in the analysis of categorical endpoints (including the primary endpoint) will use Non-Responder Imputation while incorporating Multiple Imputation (MI) to handle missing data due to COVID-19 (NRI-C).

The NRI-C will categorize any subject who does not have an evaluation during a pre-specified visit window (either due to missing assessment or due to early withdrawal from the study) as a non-responder for the visit. The only exceptions are: 1) when the subject is a responder both before and after the visit window, the subject will be categorized as a responder for the visit. 2) missing data due to COVID-19 infection or logistical restriction will be handled by Multiple Imputation. In addition, all assessments after the start of rescue medications will not be included in the analyses; as a result, subjects will be counted as non-responders thereafter and will not be imputed by MI. NRI-C will not be applied to the endpoint of improvement of daily Worst Pruritus NRS ≥ 4 up to Day 28.

- A sensitivity analysis for categorical endpoints will use NRI with No special data handling for missing due to COVID-19 (NRI-NC).

NRI-NC will be performed in the same way as NRI-C without the exception #2 above. That is, missing due to COVID-19 infection or logistical restriction will also be counted as non-responders.

Subjects whose change/percent change from Baseline cannot be calculated because of a missing Baseline will be considered as a non-responder at all post-baseline visits in both NRI-C and NRI-NC approaches. NRI-NC will be primary approach for the efficacy endpoint of improvement of daily Worst Pruritus NRS ≥ 4 up to Day 28.

- Multiple Imputation (MI), a sensitivity analysis for the primary endpoint and key secondary categorical endpoints: Markov Chain Monte Carlo (MCMC) will be first applied to augment data into monotonic missing pattern and PROC MI will be used to generate 30 datasets using the regression method. The variables to be included in the imputation model are: treatment group, stratum (vIGA-AD categories), gender, Baseline, and measurements at each visit up to the end of the analysis period. The random seed for MCMC and the random

seed for PROC MI are specified in [Appendix E](#). The imputed post-baseline measurements will be rounded to the same precision as the observed data before the determination of responder status. Subjects will be characterized as responders or non-responders based on MI imputed datasets. Using the CMH model adjusted by the stratification factor (vIGA-AD categories), the imputed endpoints will be analyzed using each of the 30 datasets. SAS PROC MIANALYZE will be used to generate the final inferences of the risk difference between upadacitinib group and dupilumab group. Note that measurements will be considered as missing after the first dose of rescue treatment before MI. Regardless of MI imputed values, subjects after receiving rescue medications will be counted as non-responders.

